9.3.4 Demographic and Baseline Characteristics

Demographic information will be summarized (n, mean, SD, minimum, maximum for continuous endpoints; n and % for categorical endpoints) by treatment group and for treatment groups combined. This will be for the Safety Analysis Set; however, if substantial difference exists between the numbers of patients in the SAF and the FAS, then a separate similar summary will be provided for the FAS.

10 ETHICS AND RESPONSIBILITIES

This study will be conducted in compliance with the protocol, Good Clinical Practice (GCP), Good Laboratory Practice (GLP) and all applicable regulations, including the Federal Food, Drug and Cosmetic Act, U.S. applicable Code of Federal Regulations (title 21), any IEC requirements relative to clinical studies. The study will also be conducted in compliance with the recommendations laid down in the most recent version of the Declaration of Helsinki, with the exception that registration of such Phase 1 trials in a publicly accessible database is not mandatory.

This study will be conducted in compliance with the protocol. The protocol and any amendments and the patient informed consent will receive Institutional Review Board/Independent Ethics Committee (IRB/IEC) approval/favorable opinion prior to initiation of the study.

All serious breaches must be reported to Biohaven (or designee) immediately. A Serious breach is a breach of the conditions and principles of GCP in connection with the study or protocol, which is likely to affect, to a significant degree, the safety or physical or mental integrity of the patients of the study or the scientific value of the study.

Study personnel involved in conducting this study will be qualified by education, training, and experience to perform their respective task(s).

This study will not use the services of study personnel where sanctions have been invoked or where there has been scientific misconduct or fraud (e.g., loss of medical licensure, debarment).

10.1 Data and Safety Monitoring Committee

This study will not make use of a Data Safety Monitoring Committee (DMC). The study medication troriluzole has been tested and found to be well tolerated. Safety will be closely monitored via the sites and procedures for unblinding in cases of emergency will be followed.

10.2 Institutional Review Board/Independent Ethics Committee

The Investigators agree to provide the IEC with all appropriate documents, including a copy of the protocol/amendments, ICFs, advertising text (if any), Investigator's brochure (if any) and any other written information provided to study subjects. The trial will not begin until the Investigators have obtained the IEC favorable written approvals for the above-mentioned study documents. A properly executed written ICF shall be read, signed, and dated by each subject prior to entering the trial or prior to performing any study procedure. The original signed and dated ICF will be kept at the Investigator site and a copy will be given to the subject.

In the event that the protocol is amended, the revised protocol must be approved by the IEC prior to its implementation, unless the changes involve only logistical or administrative aspects of the trial. If a revised ICF is introduced during the study, each subject's further consent must be obtained. The new version of the ICF must be approved by the IEC, prior to subsequently obtaining each subject's consent.

The Principal investigator and the Sponsor's representative must sign the protocol and its amendments (if any) before initiating the study.

It is the Sponsor's responsibility to submit the protocol and its amendments (if any), and the ICFs to regulatory authorities when necessary.

10.3 Informed Consent

Investigators must ensure that patients, or, in those situations where consent cannot be given by patients, their legally acceptable representatives, are clearly and fully informed about the purpose, potential risks, and other critical issues regarding clinical studies in which they volunteer to participate.

Biohaven (or designee) will provide the investigator with an appropriate (i.e., Global or Local) sample informed consent form which will include all elements required by

ICH, GCP and applicable regulatory requirements. The sample informed consent form will adhere to the ethical principles that have their origin in the Declaration of Helsinki.

Before the potential subject has undergone any study-related screening procedures, the nature of the study and the potential risks associated with it will be explained to the subject, and the subject will be given an opportunity to ask questions to his or her satisfaction. After the questions are answered, but before proceeding further, the subject must read and sign a written informed consent form. This signed informed consent form will be reviewed and approved by an IRB/IEC, revisions to the protocol and informed consent form will be reviewed and approved by the IRB/IEC, a copy retained in the Study Master File, and the date and time the subject signed the form will be entered in his or her CRF. The subject will be provided with a copy of his or her signed and dated informed consent form.

If informed consent is initially given by a patient's legal guardian or legally acceptable representative, and the patient subsequently becomes capable of making and communicating their informed consent during the study, then the consent must additionally be obtained from the patient.

The informed consent form must also include a statement that Biohaven and its representatives and regulatory authorities may have direct access to patient records.

The rights, safety, and well-being of study patients are the most important considerations and should prevail over interests of science and society.

10.4 Case Report Forms

An investigator is required to prepare and maintain adequate and accurate case histories designed to record all observations and other data pertinent to the investigation of each study patient. Data reported on the CRF that are derived from source documents must be consistent with the source documents or the discrepancies must be explained.

Electronic CRFs will be prepared for all data collections fields when EDC is being used.

The confidentiality of records that could identify patients must be protected, respecting the privacy and confidentiality rules in accordance with the applicable regulatory requirement(s).

The investigator must retain a copy of the CRFs including records of changes and corrections. If EDC is being used, signatures will be obtained electronically and a copy of the electronic CRFs will be provided (or the data from the CRFs) for future reference.

10.5 Records Management and Retention

In accordance with the principles of GCP and GLP, the study may be inspected by regulatory authorities, the Sponsor and CRO. The Sponsor is entitled to access information about the status of the study and to review the original documents of the study.

The investigator must retain all study records and source documents for the maximum required by the applicable regulations and guidelines, or institution procedures or for the period of time specified by the sponsor, whichever is longer. The investigator must contact the Sponsor prior to destroying any records associated with this study.

Biohaven will notify the investigators when the study files for this study are no longer needed.

If the investigator withdraws from the study (i.e., retirement, relocation), the records shall be transferred to a mutually agreed upon designee. Notice of such transfer will be given in writing to Biohaven.

It is the responsibility of the investigator to ensure that the current disposition record of investigational product (those supplied by the sponsor) is maintained at each study site where the study drug is inventoried and dispensed. Records or logs must comply with applicable regulations and guidelines and should include:

- o Amount of study drug received and placed in storage area;
- o Label ID number or batch number or Kit number as specified for the protocol;
- Amount dispensed to and returned from each patient;
- Amount transferred to another area or site for dispensing or storage if applicable;
- Amount of drug lost or wasted;
- Amount destroyed at the site if applicable;
- Amount returned to sponsor, if applicable;
- Retained samples for bioavailability/bioequivalence, if applicable;
- Record of dates and initials of personnel responsible for IM dispensing and accountability.

10.6 Source Documentation

An investigator is required to prepare and maintain adequate and accurate case histories designed to record all observations and other data pertinent for all subjects on study.

If source documents are created to support the collection of study information, this must be retained with the other pertinent medical record for each patient for verification of data points, unless otherwise instructed by the Sponsor or designee to enter data directly on the CRF.

10.7 Study Files and Record Retention

The CRO will utilize the Sponsor's Electronic Trial Master File (eTMF) for the purposes of this study. The Sponsor does not require original documents that have already been scanned and entered into the eTMF system be forwarded to the Sponsor. Any original documents (i.e. 1572, signed financial disclosure, signed ICF, etc.) will be retained in the regulatory binder at the study site. The CRO will do a final TMF reconciliation to ensure all study files and regulatory documents have been correctly uploaded to the TMF prior to the close or termination of the study. Any materials or documents to support the clinical trial outside of the eTMF (i.e. rater training tapes) should be maintained by the CRO. The Sponsor will be contacted to determine whether the study documents/materials that are retained outside of the TMF will be forwarded to the Sponsor, destroyed or kept at CRO or at another facility for a longer period of time at the Sponsor's expense.

11 AMENDMENTS

Protocol modifications, except those intended to reduce immediate risk to study subjects, may be made only by Biohaven. A protocol change intended to eliminate an apparent immediate hazard to subjects may be implemented immediately, provided the IRB/IEC is notified within 5 days.

Any permanent change to the protocol must be handled as a protocol amendment. The written amendment must be submitted to the IRB/IEC and the investigator must await approval before implementing the changes. Biohaven will submit protocol amendments to the appropriate regulatory authorities for approval.

If in the judgment of the IRB/IEC, the investigator, and/or Biohaven, the amendment to the protocol substantially changes the study design and/or increases the potential risk to the subject and/or has an impact on the subject's involvement as a study participant, the currently approved written informed consent form will require similar modification. In such cases, informed consent will be renewed for subjects enrolled in the study before continued participation.

12 STUDY REPORT AND PUBLICATIONS

Biohaven is responsible for preparing and providing the appropriate regulatory authorities with clinical study reports according to the applicable regulatory requirements. The publication policy of Biohaven is discussed in the investigator's Clinical Research Agreement.

13 STUDY DISCONTINUATION

Both Biohaven and the Principal Investigator reserve the right to terminate the study at the investigator's site at any time. Should this be necessary, Biohaven or a specified designee will inform the appropriate regulatory authorities of the termination of the study and the reasons for its termination, and the Principal Investigator will inform the IRB/IEC of the same. In terminating the study, Biohaven and the Principal Investigator will assure that adequate consideration is given to the protection of the subjects' interests.

[figure not shown]
14 CONFIDENTIALITY

All information generated in this study is considered highly confidential and must not be disclosed to any person or entity not directly involved with the study unless prior written consent is gained from Biohaven. However, authorized regulatory officials, IRB/IEC personnel, Biohaven and its authorized representatives are allowed full access to the records.

Identification of subjects and CRFs shall be by initials, screening and treatment numbers only. If required, the subject's full name may be made known to an authorized regulatory agency or other authorized official.

Biohaven may approve the sharing of de-identified data from this study to be made available to ataxia researchers for the purpose of advancing the understanding of SCA, rating scales, or trial methodology for the affected population. In any publication of this data, confidentiality of individual subjects will be protected.

1 INTRODUCTION

This document is an addendum to the statistical analysis plan (SAP), version 2.0, dated 6 September 2017 for protocol BHV4157-201, which is a Phase 2b/3, randomized, double-blind, placebocontrolled trial of BHV4157 in adult subjects with spinocerebellar ataxia (SCA). Reference the protocol (version 7.0, 8 July 2019) and the original SAP (version 2.0, 6 September 2017) for additional detail on the trial design and plan for statistical analysis. The purpose of this document is to provide more detail to items that are not specifically discussed in the original SAP, make corrections to the SAP, as well as include a statistical plan for any additional ad hoc analyses of interest.

3 COMPUTING ENVIRONMENT

Section 4.2.2 of the SAP referred to specific versions of the coding dictionaries; however, medical history and adverse events (AEs) are coded using the most current version of the Medical Dictionary for Regulatory Activities (MedDRA) at the time of database lock, and prior/concomitant medications are coded using the most current version of the World Health Organization Drug Dictionary (WHO-DD) at the time of database lock.

4 ANALYSIS SETS

BHV4157 cohort: Subjects that took at least one dose of BHV4157 and provided at least one post-baseline total SARA score.

- The analysis of the FAS cohort will take into account both the dosing break between phases (Randomization and Extension) and the dosing break prior to the Expanded Extension.
- The analysis of the ITT cohort will take into account the dosing break between phases (Randomization and Extension) but not the dosing break prior to the Expanded Extension.

On-treatment data for efficacy analyses are considered as any visit that occurs within 7 days (inclusive) of the post-final study treatment dose. The Final Study Visit is considered as any visit that occurs between 8 and 21 days post-final study treatment dose.

On-treatment data for safety analyses are considered as any visit or AE recorded within 30 days (inclusive) post-final study treatment dose.

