4 STUDY PLAN

4.1 Study Design and Duration

BHV4157-201 is a Phase IIb/III, multicenter, randomized, double-blind, 2-arm placebo-controlled parallel-group study designed to assess safety, tolerability, and efficacy in a population of patients with Spinocerebellar Ataxia. Subjects will be randomized to receive placebo (QD) or troriluzole (140 mg QD),

Subjects with SCA3 genotype will be limited to comprise up to approximately 10% so that this most common type of SCA is not over-represented.

Dosing will continue for 8 weeks. Subjects will return to the clinic two weeks after discontinuing study medication for a follow-up safety visit. In addition, subjects completing the Randomization Phase will be offered approximately 192 weeks of open-label treatment as long as the PI believes open-label treatment offers an acceptable risk-benefit profile. Subjects who agree to enter the Extension Phase will not complete the follow-up safety visit and should continue dosing as specified.

Subjects entering the Extension Phase would have their first Extension Visit four weeks after the Week 8 Randomization Phase visit. If there is a delay of two weeks or more in dosing between the Randomization Phase and the Extension Phase, subjects would be required to complete an Extension Baseline Visit. Thereafter, subjects will undergo visits every fourth week through Week 12 of this phase. Then subjects will undergo visits every 12 weeks up to Week 192 of this phase. All subjects will undergo a termination visit two weeks after the last dose of study drug.

Subjects who previously completed the extension phase will be allowed to participate in the expanded extension phase for a total of 144 weeks of open-label administration of troriluzole, provided the PI deems this treatment to present an acceptable risk-benefit profile. Such subjects who have been off of medication for at least 2 weeks, will need additional Baseline Visits followed by visits scheduled approximately every 12 weeks, as well as laboratory assessments at approximately 4 and 8 weeks after re-starting medication. In addition, these subjects will be required to have clinical laboratory assessment results that are not deemed clinically significant, available prior to the Baseline Visit and drawn within 6 weeks prior to that visit. These subjects should not have taken riluzole for at least 12 hours prior to re-starting troriluzole.

[figure not shown]

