4.3.3 Extension Phase (if applicable)

The Extension Phase includes a Baseline Visit; however, that visit is only required if there is a break in dosing two weeks or greater between the Week 8 Visit in the Randomization Phase and the Week 4 visit in the Extension Phase. The Extension Phase also includes a Baseline Visit 1 and Baseline Visit 2; however those visits are only required for subjects who have previously completed the 2 week post-dose visit in the Extension Phase, and who will be reentering the extension phase of open-label treatment beginning at Week 60 through Week 144. Subjects re-entering the extension phase will complete the Baseline 1 visit to confirm that they meet safety eligibility requirements, then return for the Baseline 2 visit, followed by visits scheduled approximately every 12 weeks, as well as laboratory assessments at approximately 4 and 8 weeks after re-starting medication. Thereafter, subjects will undergo visits every 12 weeks up to Week 144 of the Extension Phase (or 192 weeks for continuing subjects). All subjects will undergo a termination visit two weeks after the last dose of study drug.

Please refer to the Schedule of Assessments/Time & Events for details on procedures during the Extension Phase. There is a visit window of +/- 7 days during the Extension Phase of the study.

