4.8.2. Adverse Events

Adverse eventss will be coded using MedDRA and displayed in tables and listings by system organ class (SOC) and preferred term (PT).

Analyses of AEs will be performed for those events that are considered treatment-emergent, where treatment-emergent is defined as any AE that developed, worsened, or became serious after first dose of test treatment.

Adverse events are summarized by subject incidence rates; therefore, in any tabulation, a subject contributes only once to the count for a given AE (SOC or PT).

The number and percentage of subjects with the following on-treatment AEs will be summarized by treatment group and overall for the Randomization and Extension Phases, separately.

- Treatment-emergent AEs,
- AEs related to treatment (definitely, probably, or possibly),
- SAEs,
- AEs with Grade 2 or greater severity,
- AEs leading to discontinuation, and
- Standardized MedDRA query (SMQ) of interstitial lung disease, including eosinophilic pneumonia

On-treatment AEs are AEs with a start date prior to 30 days after the last dose of study drug. For the Randomization Phase, treatment-emergent AEs will be assessed from the date of randomization until: 1) the first day of the Extension Phase or 2) if the subject did not continue into the Extension Phase, 30 days after the last dose of study drug. For the Extension Phase, treatment-emergent AEs will be assessed from the first day of the Extension Phase until 30 days after the last dose of study drug.

In the above tabulations, each subject will contribute only once (i.e., the most related occurrence or the most severe occurrence) to each of the incidence rates in the descriptive analysis, regardless of the number of episodes. No formal hypothesis-testing analysis of AEs incidence rates will be performed.

All AEs occurring pre-treatment, during the Randomization phase, during the Extension phase, and throughout the entire study will be listed. Additional listings will be provided for the Randomization and Extension Phases, including deaths, SAEs, and AEs leading to withdrawal of study drug.

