4.8.3. Laboratory Data

Clinical laboratory evaluations include:

- Hematology: hemoglobin, hematocrit, platelets, complete blood count with differential and absolute neutrophil count
- Serum Chemistry: sodium, potassium, chloride, calcium, alanine aminotransferase (ALT), aspartate aminotransferase (AST), lactate dehydrogenase (LDH), alkaline phosphatase (ALP), gamma-glutamyl transferase (GGT), phosphorous, bicarbonate, creatine phosphokinase (CPK), total protein, albumin, total bilirubin (if greater than 2 mg/dl bilirubin will be fractionated), glucose, creatinine, blood urine nitrogen (BUN), uric acid, and pregnancy testing (for women of child-bearing potential). Additionally at screening, total cholesterol, low-density lipoprotein (LDL), high-density lipoprotein (HDL), triglycerides, folate, hemoglobin A1c (HbA1C), P-Amylase, Lipase, thyroid-stimulation hormone (TSH), and T4
- Urinalysis: pH, specific gravity, protein, ketones, glucose, blood, and microscopic exam (completed only if any part of the urinalysis is not negative)
- Additional tests: human immunodeficiency virus (HIV), hepatitis B surface antigen (HBsAg), and hepatitis C virus (HCV) antibody at screening

Clinical laboratory values will be expressed using conventional units. In the event of repeat values within the same analysis visit, the measurement closest to the target day for the analysis visit interval will be used.

On-treatment laboratory abnormalities are those with an assessment date after the date/time of first dose of study drug and within 30 days after the last dose of study drug. For the Randomization Phase, treatment-emergent laboratory abnormalities will be assessed from the date of randomization until: 1) the first day of the Extension Phase or 2) if the subject did not continue into the Extension Phase, 30 days after the last dose of study drug. For the Extension Phase, treatment-emergent lab abnormalities will be assessed from the first day of the Extension Phase, treatment-emergent lab abnormalities will be assessed from the first day of the Extension Phase until 30 days after the last dose of study drug.

The observed value and change from baseline will be summarized for each continuous laboratory parameter for the Randomization and Extension Phases, separately. In addition, the shift from baseline for laboratory abnormalities (low, normal, high) will be tabulated for the Randomization and Extension Phases, separately.

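### On the readable text the safety on-treatment window closes only once, so off-drug time beyond day 30 of a returning subject's dosing gap counts as on-treatment

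*SAP*

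**What the plan says.** The addendum, section 4 (Analysis Sets), defines the safety window by its end only: "On-treatment data for safety analyses are considered as any visit or AE recorded within 30 days (inclusive) post-final study treatment dose". SAP 4.8.2 gives a similar rule for adverse events: "On-treatment AEs are AEs with a start date prior to 30 days after the last dose of study drug". For the Extension Phase it adds that "treatment-emergent AEs will be assessed from the first day of the Extension Phase until 30 days after the last dose of study drug". SAP 4.8.3 labels a laboratory abnormality on-treatment if it has an "assessment date after the date/time of first dose of study drug and within 30 days after the last dose of study drug". None of these sentences excludes an off-drug interval.

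For the Randomization Phase, SAP 4.8.2 ends the treatment-emergent window at "1) the first day of the Extension Phase or 2) if the subject did not continue into the Extension Phase", and only in the second case does the limit of 30 days after the last dose apply. SAP 4.8.3 repeats this for laboratory data.

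The plan knows that dosing can be interrupted. The same addendum section says of efficacy: "The analysis of the FAS cohort will take into account both the dosing break between phases", and goes on to name the break before the Expanded Extension as well. Protocol 4.3.3 describes who re-enters: Baseline Visits 1 and 2 are "required for subjects who have previously completed the 2 week post-dose visit in the Extension Phase" and who then resume open-label treatment. Protocol 4.1 puts the time off drug at 2 weeks or more and gives no upper limit.

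**The concern.** By the plan's own standard, a finding more than 30 days after dosing stops is off-treatment. A window that closes only after the final dose of the whole study breaks that standard for anyone who stops and later restarts. Whether a result counts as on-treatment then depends on something that happens after it was obtained.

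The label has uses. Addendum sections 8 and 12 rely on it for the events of special interest (low neutrophil count, ALT or AST above 3x ULN, and that elevation together with raised bilirubin), and section 8 uses those events to select subjects for narratives. SAP 4.8.2 uses it for the adverse event tables. The addendum also keys on when an event was recorded, whereas SAP 4.8.2 keys on its start date. An event that began in the gap and was reported after restart is on-treatment under either wording.

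**Working it through.** The plan states no figure on this point that could be reproduced. The check compares the rules and then does date arithmetic.

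**Inputs**
- Window end: final or last dose plus 30 days (addendum 4; SAP 4.8.2, 4.8.3).
- Meaning of last dose in the Extension: SAP 4.8.1 (exposure) ties it to the end of the study or withdrawal, not to each stretch of dosing.
- Gap in returning subjects: at least 14 days, no maximum (protocol 4.1).
- Samples before restart: Table 5 marks laboratory assessments at Baseline 1 and Baseline 2. Drug is first dispensed at Baseline 2. Its footnotes make Baseline 2 laboratory work mandatory only if that visit is more than 7 days after Baseline 1, and allow a repeat of Baseline 1 samples with sponsor permission.
- Qualifying samples must be drawn within 6 weeks before the Baseline Visit (protocol 4.1).

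**Step 1: the same result in two subjects.** Both have a sample on day 60 after their last Extension dose.
- Subject A does not restart. The final dose is day 0 and the window ends on day 30. Since 60 > 30, the result is off-treatment.
- Subject B restarts on day 90. The final dose is after day 90, so the window ends after day 120. Since 60 < 120, the result is on-treatment.

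**Step 2: days misclassified.** The first 30 days of a gap are on-treatment under a per-interval rule too. For a gap of g days, the misclassified part is max(0, g − 30). The gap lengths below are assumptions, except the 14-day minimum.

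| Gap g (days) | max(0, g − 30) |
|---|---|
| 14 | 0 |
| 30 | 0 |
| 42 | 12 |
| 60 | 30 |
| 90 | 60 |
| 180 | 150 |
| 365 | 335 |

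**Step 3: which samples are affected.** Assume that dosing restarts on the Baseline Visit at which drug is dispensed. The earliest qualifying sample is then drawn on day g − 42 of the gap. It lies beyond day 30 when g − 42 > 30, that is g > 72. Above 72 days every qualifying sample is misclassified. Between 31 and 72 days it depends on the draw date. At 30 days or less none is.

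**Step 4: Randomization Phase.** For a break of b days after the last randomized dose, the window runs b days if the subject continues and 30 days if not. The excess is max(0, b − 30). Protocol 6.2.4.5 postpones Extension dosing when laboratory abnormalities are potentially clinically significant, so a longer break is possible in subjects with a laboratory signal.

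**The case against.** The case for leaving this alone has real substance.

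- **Eligibility screening removes most marked abnormalities.** Returning subjects need laboratory results that are not considered clinically significant, and Baseline 2 takes place only if Baseline 1 meets the eligibility criteria. A subject who fails Baseline 1 and never restarts is handled correctly. This stands. What remains is a value over a special-interest threshold that was judged not clinically significant, an abnormal sample later replaced by an acceptable repeat, or a Baseline 2 sample.
- **Adverse event capture in the gap is thin.** Table 5 marks no adverse event assessment at Baseline 1 or 2, and protocol 8.1.3 ends routine SAE collection 30 days after dosing stops. This also stands.
- **The final dose may be meant per phase.** The addendum places the Final Study Visit 8 to 21 days after that dose, which fits the 2-week visit that returning subjects had already completed. SAP v2.0, dated 6 September 2017, describes only a 48-week Extension, so its last dose was not written with re-entry in mind. A per-phase reading is plausible and would close the window during the gap. No readable sentence adopts it, and SAP 4.8.1 points the other way. It would not repair the treatment-emergent rule for the Randomization Phase, which runs expressly to the first Extension day.
- **The addendum is only partly readable.** Section 10, on updates to the SAP analyses, shows no content, and a safety rule for gaps could sit there. This limits confidence.
- **The SAP does recognise the first break.** SAP 4.8 resets the Extension baseline after 14 days or more. That governs change from baseline, not whether a finding is on-treatment.

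**Conclusion.** The point holds on the readable text, with moderate confidence. The safety window closes once, so off-drug time beyond day 30 of a returning subject's gap is on-treatment only because the subject later restarted. The Randomization Phase treats subjects who continue differently from those who do not. The practical effect is probably small: it is limited to gaps or breaks longer than 30 days, and for returning subjects mainly to pre-restart samples that can feed the special-interest events and narratives, plus gap adverse events recorded later.

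Two stronger readings are tempting, and the documents do not support them.

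- A reader might express the misclassified days as a share of planned on-drug days and treat that share as bias. The gap lengths are not given, SAP 4.8.2 counts each subject once per event, and no readable section plans person-time rates. Such a percentage would correspond to no planned table.
- A reader might infer from the protocol's re-entry condition, "These subjects should not have taken riluzole for at least 12 hours prior to re-starting troriluzole", that raised transaminases before restart reflect riluzole and would be charged to troriluzole. The condition does not show that any returning subject took riluzole, and addendum section 8 calls for narratives whatever the relationship to study drug. The point does not need that inference.

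**What to change.** In addendum section 4 and SAP 4.8.2 and 4.8.3:

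1. Define safety on-treatment time per dosing interval (Randomization, Extension, Expanded Extension after re-entry). Each interval runs from its first dose to the earlier of 30 days after its last dose or the first dose of the next interval.
2. Classify adverse events by onset date and laboratory results by collection date, and replace the reference to recording.
3. Flag Expanded Extension Baseline 1 and 2 results, including repeats, as pre-restart values. Count them as on-treatment only if they fall within 30 days of the previous interval's last dose.
4. List events and abnormalities outside the window separately as off-treatment, so that nothing is lost from view.

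If a per-phase final dose was always intended, the same wording makes that explicit. The cost is a text change and minor reprogramming from dosing dates already collected. No new data are needed. The downside is that a few events may move from on-treatment tables to an off-treatment listing.
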